## 6.2. Derivation and Conversion of Data

- 1 Duration of type II diabetes (Month) = (Date of ICF – Initial Diagnosis Date +1)/30.4375, present to 1 decimal places (dp).
- 2 Diabetes treatment Days = End date – Start date + 1
- 3 Duration of medical history = End date – Start date + 1
- 4 Duration of adverse events (days) = End date – Start date + 1
- 5 For subjects followed up in the study, “planned dosage” stands for the planned total dose that should be taken in certain periods (e.g. run-in or treatment periods). If early withdrawal from the study occurs, the planned dosage stands for the total dose that should be taken from beginning of that period to the last day of administration. Actual dosage means dispensed tablets - returned tablets – missed tablets (must be verified and consistent with the records in subject diaries. If not, details of actual drug usage should be checked and recorded).

Dosing records of run-in period, double-blind treatment period and open-label treatment period will be summarized respectively.

6 Actual dosing exposure: actual dosing duration (Day) \* actually daily dose (piece / day),

$$\text{Percentage of Drug Compliance} = \frac{\text{Actual Dosage}}{\text{Planned Dosage}} \times 100\%.$$

Compliance of run-in period, Double-blind treatment period and open-label treatment period will be calculated.

7 For continuous parameters in laboratory test. If value is lower than the lower limit of detection, then impute with  $\frac{1}{2}$  of the lower limit of detection. If value is higher than the upper limit of detective, then impute with the 1.1 times that of upper limit of detective.

8 Function of  $\beta$  cell will be calculated using below formula,

Name	Formula
I0/G0	FINS / FPG
$\Delta I30/\Delta G30$	(INS30-FINS) / (PG30-FPG)
$\Delta C30/\Delta G30$	(CP30-FCP) / (PG30-FPG)
$\Delta I120/\Delta G120$	(INS120-FINS) / (PG120-FPG)
HOMA- $\beta$	20 * FINS / (FPG-3.5)
HOMA-IR	FINS * FPG / 22.5
Disposition Index(DI)	$(\Delta I30/\Delta G30) / \text{HOMA-IR}$

FINS: Fasting Insulin (mU/L); INS30: 0.5-hour Postprandial Insulin (mU/L); INS120: 2-hour postprandial insulin; FPG: Fasting Plasma Glucose (mmol/L); PG30: 0.5-hour Postprandial Plasma Glucose (mmol/L); PG120: 2-hour Postprandial Plasma Glucose (mmol/L); FCP: Fasting C-Peptide (pmol/L); CP30: 0.5-hour postprandial C-Peptide (pmol/L);

Insulin: 1 mU/L = 1 uIU/mL.

HOMA2- and HOMA2-IR will be calculated using HOMA2 Calculator.

### 6.3. Definition of Baseline and Change from Baseline

The last non-missing value before first double-blind dose administration will be used as baseline in efficacy and safety endpoints in double-blind treatment period. The last non-missing value before double-blind treatment drug exposure and at the end of double-blind treatment period are respectively used as the baseline of efficacy evaluation for whole study. If either the baseline value or the post-baseline value is missing, then set change from baseline as missing.

$$\text{Change from Baseline} = \text{Post-Baseline Value} - \text{Baseline Value}$$

## 6.4. Multiple Measurement

For data of scheduled visit in summary analysis, if there are multiple values in a same scheduled visit, then the last one will be taken.

In listing, all values in scheduled and unscheduled visit will be displayed. If there are multiple values in one visit, then all will be displayed.

## 6.5. Data Display

Analysis dataset will be created according to CDISC standard, e.g. date and description in SDTM and ADaM will be displayed with ISO 8601 format (YYYY-MM-DD).

Listings will be classified by treatment group, center ID, subject ID and visit or date if appropriate.

All data will be processed, summarized and analyzed using SAS® Statistical Package Version 9.4 or a later release (Windows OS).

Following descriptive statistics will be presented in the summary table of continuous variables.

**Table 2 Specification of Number of Decimal Places for Descriptive Statistics**

Label	Description	No. of decimal places (dp)
N	Number of subjects in the treatment group	Always present to 0 dp
n	Number of subjects with non-missing values	Always present to 0 dp
Mean	Arithmetic Mean	1 dp more than raw data
SD	Standard Deviation	2 dp more than raw data
Median	Median	1 dp more than raw data
Q1	1 st quartile	1 dp more than raw data
Q3	3 rd quartile	1 dp more than raw data
Min	Minimum	Same as raw data
Max	Maximum	Same as raw data

Following statistical parameter will be presented in the summary table of statistical analysis.

**Table 3 Specification of Number of Decimal Places for Statistical Analysis**

Label	Description	No. of decimal places (dp)
LS Mean	Mean adjusted by treatment groups	1 dp more than raw data
Standard Error	Standard Error	2 dp more than raw data
Difference	Difference compared with placebo	1 dp more than raw data
95% CI	95%CI of difference/ratio between treatment groups	The same dp as difference or ratio
p-value	p-value	3dp (or <0.001, or >0.999)

The maximum decimal places (dp) is 4 for data displaying.

## 6.6. General rule of End-Of-Treatment Visit and Unscheduled Visit

For efficacy endpoint, if no scheduled visit value is missing, then corresponding unscheduled visit will not be included in analyses, otherwise the corresponding unscheduled visit will be used for missing data imputation (eg. LOCF). End-of-treatment visit of drop-out subjects will be mapped to nearest scheduled visit. Both of conventions below will be followed in determination.

1. The gap between end-of-treatment visit and nearest scheduled visit  $\leq 7$  days
2. Drug discontinuation before end-of-treatment visit  $\leq 7$  days.

For safety endpoint, if scheduled visit value is missing and followed by a consequent unscheduled visit, then the data at the nearest consequent unscheduled visit will be mapped on the corresponding missing scheduled visit (eg. LOCF). For the subjects who discontinued from the study early, end of trial (EOT) data will be mapped to the next scheduled visit.

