## 8.6 Database Lock

Two stages are planned for database lock in this study.

The first database lock is scheduled at the completion of the double-blind treatment for all subjects. After the blinded data review meeting, the principle investigator, sponsor, and biostatistician must sign off all related documents before the database lock (DBL). DBL is limited to the double-blind treatment data, but not the data in the open-label treatment period. No update is permitted to locked data in principle. Errors found after DBL should be evaluated to determine whether database unlock is necessary for data correction. Documentation must be recorded if database unlock is required.

The second database lock is scheduled at the completion of the open-label treatment. A regular data review meeting is required before the final DBL. The investigator, sponsor, and biostatistician should sign off relevant documents before DBL. In principle, no update is permitted to locked data. Errors found after database lock should be evaluated to determine whether database unlock is necessary for data correction. Documentation must be recorded if database unlock is required.

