### **9.3.3 Efficacy Analysis for Secondary Endpoints**

The secondary efficacy endpoints include changes from baseline at the end of double-blind period (at Week 24) of 2h PPG, and FPG. The same analysis method for the primary efficacy endpoint is used, i.e. MMRM. The adjusted least-squares mean difference between HMS5552 and placebo, and its 95% CI is estimated by MMRM.

HbA1c response rate is calculated based on the data imputed by last observation carried forward (LOCF). The HbA1c response rate, i.e. number and percentage of subjects whose HbA1c is less than 7.0% at the end of double-blind treatment period (at Week 24) are summarized. The HbA1c response rate and 95% CI for each group are estimated using the logistic regression method.

The measurement and changes of HbA1c, FPG and 2h PPG from the end of double-blind period (Week 24) to the end of study (Week 52) are summarized by two groups: one group is for subjects who are randomized into HMS5552 treatment group, and the other group is for subjects who are randomized into placebo group while switched to HMS5552 open-label treatment after double-blind period (Week 24). The measurements at the end of double-blind period (Week 24) are used as baseline for the summary of the measurements and change from baseline at each visit in the open-label period.

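### SAP 6.6 carries a later unscheduled safety value back to a missed visit with no time limit and no stop at the end of the double-blind period, and labels this LOCF

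*Supplement*

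**What the plan says.** SAP 5 makes section 6.6 the mapping rule for all by-visit summaries. For safety it has two parts.

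- **Missed visit.** The trigger is "For safety endpoint, if scheduled visit value is missing and followed by a consequent unscheduled visit". The action is that "the data at the nearest consequent unscheduled visit will be mapped on the corresponding missing scheduled visit (eg. LOCF".
- **Early discontinuation.** For these subjects, "end of trial (EOT) data will be mapped to the next scheduled visit".

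Neither part states a number of days or a treatment period.

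The efficacy rule in the same section differs. It limits "The gap between end-of-treatment visit and nearest scheduled visit" to 7 days and adds a second 7-day limit on the time since study drug was stopped.

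Two other provisions decide where this matters. Protocol 9.3.3 describes subjects "randomized into placebo group while switched to HMS5552 open-label treatment after double-blind period (Week 24". Protocol 8.6, on the first database lock, says "DBL is limited to the double-blind treatment data, but not the data in the open-label treatment period". SAP 3.1 runs the 24-week registration analysis on that lock. SAP 3.2 bases the final analysis on all data from both periods.

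**The concern.** A by-visit safety table is read as the state of each arm at that week. Under the rule as written, a row can hold a value measured long after its nominal week. Once the placebo arm has switched, it can also hold a value measured on a different treatment.

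The protocol's own procedures show how. Suppose a placebo subject has no Week 24 ALT, starts open-label HMS5552, and at Week 28 has an ALT above 3×ULN without meeting the withdrawal criteria. Protocol Appendix 6 calls for a retest within 48 hours of the report. If that retest is the first unscheduled visit after Week 24, SAP 6.6 puts it in the Week 24 row, passing over the valid Week 28 visit. Off-schedule tests prompted this way follow abnormal results, so back-filled values may lean towards abnormal ones. The documents give no figures on that.

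The label is a separate problem. SAP 6.1 defines LOCF as carrying the last available on-treatment value forward. A programmer who follows the label and one who follows the sentence would build different datasets.

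**Working it through.** **The plan's own figure.** The plan gives no figure on this point. Its one design figure, 91.4% power, reproduces: 0.4 / (1.2 × √(1/150 + 1/300)) = 0.4 / 0.12 = 3.33, and a noncentral t with 448 df gives 91.4%. Nothing here changes it.

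**Limits side by side.**

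| Rule | Direction | Time limit | Period limit |
|---|---|---|---|
| LOCF (SAP 6.1) | forward | none | on-treatment values |
| Efficacy end-of-treatment (SAP 6.6) | nearest visit | 7 days, and 7 days since drug stopped | none |
| Safety, missed visit (SAP 6.6) | backward | none | none |
| Safety, early discontinuation (SAP 6.6) | next visit | none | none |
| Double-blind TEAEs (SAP 9.3.2) | by onset or worsening | not applicable | stops at end of double-blind period |

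The early-discontinuation rule moves values forward, so it cannot carry one back across Week 24. The missed-visit rule can.

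**Longest gap allowed.** Gap = last possible study day − 7 × scheduled week. The last day is 364 + 6 = 370 in the final analysis. In the first analysis it is 168 + 4 = 172, the end of the Week 24 window.

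- Week 4, first analysis: 172 − 28 = 144 days (20.6 weeks)
- Week 4, final analysis: 370 − 28 = 342 days (48.9 weeks)
- Week 20, first analysis: 172 − 140 = 32 days (4.6 weeks)
- Week 20, final analysis: 370 − 140 = 230 days (32.9 weeks)
- Week 24, final analysis: 370 − 168 = 202 days (28.9 weeks)

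The protocol's visit windows are ±4 days up to Week 28 and ±6 days from Week 34 to Week 52.

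**Can a value cross treatments?** In the first analysis, no: the lock leaves open-label data out. In the final analysis, yes: both periods are in the data, and SAP 6.6 has no condition that stops the mapping.

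**Likely size.** The documents give no missing-data rate, so the rates here are assumptions. Suppose 3% of control subjects lack a Week 20 or Week 24 safety value and 20% of those have a later unscheduled test. With 150 to 188 controls (planned number and ceiling), 0.03 × 150 = 4.5 and 0.03 × 188 = 5.6. Multiplied by 0.2, that is 0.9 to 1.1 subjects per parameter.

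If a fraction f of placebo-origin values at a visit were taken at full drug effect, the difference shown would be (1 − f) of the true one:

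- f = 0.03 × 0.2 = 0.6%: 99.4% of the true difference
- f = 1% (1.5 to 1.9 subjects): 99%
- f = 5% (7.5 to 9.4 subjects): 95%
- f = 10% (15 to 18.8 subjects): 90%

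**The case against.** The best defence is that the rule means something narrower. A consequent visit that is nearest to the corresponding missed visit reads most naturally as a make-up visit, and a sensible programmer would not fill Week 4 from Week 20. That is probably the intent. But nearest only chooses among later visits; it does not limit how far away the chosen one may be. The 7-day limits written for efficacy in the same section are absent here.

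The defence is also right that little depends on these cells. Safety analysis is descriptive under protocol 9.3.4, although SAP 9.3.5 also models weight change by ANCOVA. Clinically significant laboratory abnormalities are reported as adverse events with dates, and hypoglycaemia is counted by event and time interval. SAP 5 and 6.4 list every scheduled and unscheduled value, so the true date stays visible.

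Two stronger readings are tempting, and the documents support neither.

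- **Open-label values counted as double-blind placebo results.** A reader might infer this from SAP 6.6 alone. Protocol 8.6 keeps open-label data out of the lock on which the placebo-controlled comparison is run. In the whole-period tables, SAP 5.4 labels the arm Placebo - HMS5552. There the visit row can be wrong, but the arm label is not.
- **An end-of-treatment value displacing an observed Week 24 efficacy value.** SAP 6.6 says "End-of-treatment visit of drop-out subjects will be mapped to nearest scheduled visit", and SAP 6.4 says "if there are multiple values in a same scheduled visit, then the last one will be taken". A reader might combine the two for a subject who leaves within days of starting open-label drug. The SAP does not say that a mapped value competes with an observed one, and protocol 8.6 in principle bars changes to locked data.

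**Conclusion.** The point holds as a defect in a stated rule, at minor severity. Followed literally, SAP 6.6 gives misplaced by-visit safety cells in both analyses. In the final analysis it can also place open-label HMS5552 values in rows up to Week 24 of the Placebo - HMS5552 arm. The LOCF label contradicts the action it describes.

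The reach is limited to by-visit laboratory, vital-sign, weight and ECG summaries. The TEAE counts and the primary HbA1c analysis are unaffected, and open-label values do not reach the first-lock comparison. The gaps of up to 144 days (first analysis) and 342 days (final analysis) are what the text permits, not what is expected. The estimate of about one control subject per parameter rests on assumed rates of 3% and 20%. Even f = 5% would dilute a visit difference by only 5%.

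**What to change.** In SAP 6.6, limit the safety rule in two ways and correct its label:

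- **Window.** An unscheduled safety value may fill a missing scheduled visit only if it lies within a stated window of that visit. One choice is to require that it be nearer to that visit than to any other scheduled visit. That allows at most 14 days between 4-week visits (28 / 2) and 21 days between 6-week visits (42 / 2). The sponsor may prefer another limit, provided it is written down.
- **Same period.** The value must come from the same treatment period as the visit it fills. No value taken after the first open-label dose may be mapped to a visit up to Week 24. Defining the period by that dose date also settles where an unscheduled repeat shortly after Visit 10 belongs.
- **Label.** Delete the LOCF example from the safety rule.

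The cost is a sentence or two in the SAP and one date condition in the analysis datasets. A few by-visit cells will stay missing. No endpoint, model or sample size changes.

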**4.5.2 Withdrawal due to Hyperglycemia**

Between Visits 2 and 15, subjects should carry out SMBG according to SMBG guidance (refer to Appendix 4 for procedures of SMBG). Subjects should contact the Investigator timely if plasma glucose exceed the value specified in SMBG guidance. Depending on the fingertip plasma glucose values, diet and exercise condition, the Investigator determines whether the subjects should return to study sites in advance for laboratory tests.

If a subject has a FPG value reaching the following criteria twice (at least once tested in the central laboratory) without any apparent causes at two consecutive visits, the Investigator will evaluate whether the subject will withdraw from the study with the reason recorded as hyperglycemia based on subject's actual situation.

1. Day 1–before Week 12: venous FPG (central laboratory)  $\geq 13.3$  mmol/L
2. Week 12–before Week 24: venous FPG (central laboratory)  $\geq 11.1$  mmol/L
3. Week 24–Week 52: venous FPG (central laboratory)  $\geq 11.1$  mmol/L.

If a subject is confirmed to withdraw from the study due to hyperglycemia, the subject must complete termination visit before withdrawal (refer to Section 4.6). Then, the study medications can be discontinued and routine diagnosis and treatment can be started.

The Investigator must ensure no other causes can be identified to explain poor glycemic control except for lack of efficacy (e.g., acute inflammations/infections, concomitant treatments, etc.). If the disease aggravation is unexpected progression, it should be reported as an AE.

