**4.5.3 Withdrawal due to Abnormal Liver Function**

Depending on the subject's condition, study treatment can be discontinued if any of the following criteria is met (no need to wait for the retest results):

- ALT or AST  $> 8 \times$ ULN
- ALT or AST  $> 5 \times$ ULN and lasts for  $\geq 14$  days

- ALT or AST  $> 3 \times \text{ULN}$  and TBiL  $> 2 \times \text{ULN}$
- ALT or AST  $> 3 \times \text{ULN}$  with liver damage symptoms (e.g., fatigue, nausea, vomiting, right upper abdominal pain or tenderness, fever, rash) or eosinophilia increase.

Active intervention or treatment needs to be given to subjects. The causes for abnormal liver function need to be identified. Consultation with hepatologists will be conducted if needed. Subjects with abnormal liver function are closely followed up until the liver function restore or the results return to baseline level. The termination visit should be scheduled as soon as possible within 3 days after discontinuation of study treatment. AEs relevant to abnormal liver function need to be recorded in time. SAEs which meet the criteria should be reported immediately.

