#### **4.6 Procedures for Subject Withdrawal**

All subjects who withdraw from the study are kept under medical monitoring. The reasons for withdrawal need to be confirmed by contacting the subject or the relatives by phone or email. If withdrawal occurs during the treatment period, the efficacy and safety observations and assessments (same as Visit 15) at the termination visit need to be completed as much as possible within 7 days (including the seventh day) after the last dose of study medications. Safety assessment via phone within 1 week after the last dose of study medications also needs to be completed. If the study treatment has been discontinued by subjects for more than 7 days before the withdrawal, the assessments (same as Visit 15) at termination visit is strongly recommended to be completed. If study treatment has been discontinued at the termination visit, the MMTT can be cancelled.

For subjects who withdraw early from the study, a comprehensive evaluation is conducted to find the reasons for early withdrawal. Withdrawal reasons should be recorded in detail. For example, the Investigator should ask about the reasons for informed consent withdrawal, rather than just to record the withdrawal.

If the early withdrawal from study is due to AEs or abnormal laboratory results, the details should be recorded on eCRF. AEs are recorded and followed up (see Section 7.2). Subject diaries and all study medications should be returned.

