## 5. General Conventions of Statistical Analysis.

Two efficacy and safety statistical analysis will be performed for double-blinding period and the whole treatment period (at most to 52nd week) independently.

For categorical variables, the number and percentage of subjects for each category are calculated. For continuous variables, the descriptive statistics such as sample size (n), mean, standard deviation (SD), median, 1st quartile, 3rd quartile, minimum, and maximum are provided.

Unless otherwise specified, the significant level for between-group comparison is set as 0.05 (two-sided).

Efficacy analysis will be conducted according to the intention-to-treat (ITT) approach. All randomized subjects will be included in the intended treatment group no matter what happens (eg drop-out or treated incorrectly).

Analysis will be summarized by visit (See chapter 6.6 for detailed mapping rules). Data observed in all visits, including scheduled visit, unscheduled and end of treatment visit will be listed and sorted by treatment group, study center, subject ID and visit (if available).

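### For early discontinuers, SAP 6.6 moves final-visit safety values to the next scheduled visit with no limit on visit gap or time off drug, so off-drug values can appear in treatment-period visit rows

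*Supplement*

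**What the plan says.** SAP section 6.6 sets the two rules next to each other.

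- **Efficacy:** "End-of-treatment visit of drop-out subjects will be mapped to nearest scheduled visit. Both of conventions below will be followed in determination". The two conditions are "The gap between end-of-treatment visit and nearest scheduled visit" of at most 7 days, and "Drug discontinuation before end-of-treatment visit" of at most 7 days.
- **Safety:** "For the subjects who discontinued from the study early, end of trial (EOT) data will be mapped to the next scheduled visit". No limit on gap or on time off drug follows.

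SAP section 5 makes this mapping operative: "Analysis will be summarized by visit (See chapter 6.6 for detailed mapping rules". Section 9.3.5 then describes vital signs, weight and BMI at each visit, and section 9.3.7 summarises categorical laboratory parameters for each visit. Protocol v1.1 section 9.3.4 also plans by-visit safety summaries.

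Protocol section 4.6 aims for the termination visit within 7 days of the last dose. It also covers the later case, "If the study treatment has been discontinued by subjects for more than 7 days before the withdrawal", and strongly recommends the assessments there too. The schedule notes in the protocol and the SAP say much the same. None of these places gives a latest acceptable time.

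Two withdrawal routes have tighter timing. For hyperglycemia, "the subject must complete termination visit before withdrawal" (section 4.5.2), and drug is stopped afterwards. For abnormal liver function, "The termination visit should be scheduled as soon as possible within 3 days after discontinuation of study treatment" (section 4.5.3).

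**The concern.** A by-visit safety table is read as showing what subjects looked like at about that week on the assigned regimen. A value taken weeks after the last dose, and then carried forward to a visit the subject never attended, is wrong on both counts. In its efficacy rule the SAP itself treats more than 7 days off drug as enough to refuse the mapping, and it gives no reason for dropping that limit for safety. At stake is the accuracy of the vital-sign, weight and laboratory rows at individual visits, and at the period boundary the treatment label as well.

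**Working it through.** The plan states no figure for this point, so the check consists of reading the rules and counting days.

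**Inputs**
- Nominal visit days (protocol section 3.5): 28, 56, 84, 112, 140, 168, 196, 238, 280, 322, 364. Spacing is 28 days to Week 28 and 42 days after that.
- Efficacy limits (SAP 6.6): gap at most 7 days and time off drug at most 7 days. Safety limits: none.
- Time off drug at the termination visit (protocol 4.6): target at most 7 days, no maximum.
- Assumption for the averages only: termination visits fall evenly over the days between scheduled visits.

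**Step 1: how far a value moves.** Forward shift = day of next scheduled visit − day of termination visit.
- Full 28-day interval: 27 intermediate days, shifts of 1 to 27, mean (1 + 27)/2 = 14 days. Shifts above 7 days: 20/27 = 74%.
- 42-day interval: 41 intermediate days, shifts of 1 to 41, mean (1 + 41)/2 = 21 days. Shifts above 7 days: 34/41 = 83%.
- The efficacy gap limit, measured to the nearest visit, accepts the first and last 7 days of an interval: 14/27 = 52% and 14/41 = 34%.

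These figures describe the visit label and apply to on-drug and off-drug values alike.

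**Step 2: time off drug.** Days from last dose to the reported visit = days off drug at the termination visit + forward shift.
- Example: last dose Day 115, termination visit Day 145. Off drug: 145 − 115 = 30 days. Next visit: Day 168, a shift of 23 days. The value is reported at Week 24, 30 + 23 = 53 days after the last dose.
- Under the efficacy rule the nearest visit is Day 140, 5 days away, so the gap passes. The 30 days off drug fail, and the value is not mapped.

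**Step 3: the period boundary.**
- Example: a placebo subject with last dose Day 150 and termination visit Day 175. Off drug: 25 days. The next scheduled visit is Week 28 (Day 196), a shift of 21 days.
- Week 28 is an open-label visit, and SAP section 5.4 labels that arm as placebo followed by HMS5552. This subject never took HMS5552.

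**Step 4: other safeguards.** No other SAP rule flags or removes off-drug safety values from the by-visit summaries. Section 6.7 adds that exposure to prohibited medication does not alter the safety assessment. Sections 5 and 6.4 keep every value in the listings, but the listings do not change the summary rows.

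**The case against.** The strongest reply is that safety and efficacy were given separate rules on purpose: an inclusive safety rule keeps each discontinuer's last assessment in view. Most termination visits should also be early, since hyperglycemia withdrawals are seen before drug is stopped, liver withdrawals within 3 days, and the rest are targeted within 7 days. Earlier on-drug values stay at their own visits, and all values are listed. Laboratory and ECG abnormalities that are new, worsened or lead to stopping must be recorded as adverse events (protocol 7.1.3) and are analysed separately.

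Much of this stands, and it rules out three stronger readings.

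- **Dilution of the HMS5552 results.** A reader might infer that adverse-event and liver withdrawals contribute recovered values while placebo hyperglycemia withdrawals do not. The 3-day and 7-day timings put most such visits inside the limit proposed here. The documents do not show recovery within those windows, nor do they link subjects more than 7 days off drug to adverse events or to either arm.
- **Individual shifts wholly corrupted.** The mapping overwrites no earlier value. The ECG and laboratory normal/abnormal comparisons run from baseline to post-treatment, so a wrong week label alone does not change them.
- **A known share of affected values.** Spreading the 20% allowance in the sample-size section over six visits gives 20%/6 = 3.3% per visit. That treats a planning allowance as a drop-out rate, assumes even timing and full attendance, and counts on-drug values too.

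The reply does not explain why an off-drug value should sit in a treatment-period visit row. Keeping all safety data does not require it, because a separate row keeps them as well.

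**Conclusion.** The point holds as a limited defect in a stated rule. Because the safety rule has neither of the limits set for efficacy, off-drug vital-sign, weight and laboratory values can be summarised at a treatment-period visit up to 27 days after measurement, or 41 days in the six-week intervals. Time off drug itself has no ceiling, and at the period boundary a placebo subject can land in an open-label row. The wording is can, not will: the SAP does not label these rows as on-treatment, and many termination visits will be timely.

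The share of affected values is not known, the effect on means is probably small, and no direction of bias between arms is established. Adverse-event tables and the primary HbA1c analysis are untouched.

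This rests on three assumptions: EOT in the safety sentence, which the SAP spells out as end of trial, means the termination visit; the next scheduled visit is read literally; and visits are counted at their nominal days.

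**What to change.** Amend the safety paragraph of SAP 6.6. Map a final-visit safety value to a scheduled visit only if it was taken no more than 7 days after the last dose and no more than 7 days from that visit. Summarise all other final-visit values in a separate early-termination row, split into at most 7 and more than 7 days since last dose, so that no safety data are dropped.

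The cost is a change of SAP wording, one extra table row, and slightly fewer values at some visits. Data collection and sample size do not change.
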